5.13.2.2 OS and OS at 1 Year for Cohorts A and B

OS and OS at one year will be analysed using the ITT set and analysis will be repeated for the PPS for Cohort A only.

OS is defined in months as the time between Visit 1 and the date of death from any cause (date of death – date of Visit 1 + 1).

OS will be calculated for the entire study duration where subjects without a death date will be right censored at the date the subject was last known to be alive (during or post study). Post-study survival information is collected until database lock, for subjects completing or withdrawing from the study.

OS will also be calculated for subjects at one year, where subjects without a death date will be right censored on the date of Visit 1 + 365 days.

Summaries of OS

Descriptive statistics will be presented for OS for the whole study period and repeated for OS at one year. The number and percentage of subjects that are censored will be summarised, along with KM estimates for the 25th, 50th and 75th percentiles for both OS and OS at one year and corresponding 95% CIs for each. OS and OS at one year will also be presented graphically using a KM plot. The proportion of subjects alive at 3 monthly intervals will also be presented.

Survival status and death details (during or post study) will be listed for each subject.

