## **5.2.2 Secondary Endpoints**

The secondary endpoints of this study, to provide further information on the safety and efficacy of the IMM-101 + nivolumab combination, are assessed at the end of the study and measured by:

Progression-free survival (PFS) assessed by RECIST 1.1. PFS is defined as the time between the date of the first post-Screening visit (Week 0, Visit 1) and the first date of documented progression, as determined by the Investigator from CT or MRI scan, or death due to any cause, whichever occurs first. Subjects who die without a reported progression will be considered to have progressed on the date of their death. Patients who did not progress or die will be censored on the date of their last evaluable tumour assessment. Patients who did not have any on study tumour assessments (scans) and did not die will be censored on their date of first post-Screening visit. Patients in cohort B who change therapy on study to IMM-101 + ipilimumab without documented progression by RECIST 1.1 will be censored at the date of their last evaluable tumour assessment prior to this change in therapy.

Overall survival (OS) and OS at 1 year. OS is defined as the time from enrolment (date of the first post-Screening visit (Week 0, Visit 1) to death due to any cause. Patients without a death date will be censored at the date the patient was last known to be alive. The median OS (if applicable) and OS rate at 12 months will be estimated.

- Incidence and frequency of laboratory parameter abnormalities
- Change from baseline values in laboratory parameter values
- Incidence and frequency of local injection site reactions.

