#### 6.7 WITHDRAWAL OF CONSENT

Patients who request to discontinue study treatment can remain in the study and continue to be followed for protocol specified follow-up procedures unless the patient wishes to withdraw from study procedures as well as from study treatment. If a patient should wish to withdraw consent for future follow-up (as in Section 6.4) they should notify the Investigator of this decision. The withdrawal of consent should be explained in the medical records by the Investigator, to confirm whether the withdrawal is from further treatment with study drug only, or also from study procedures and/or post treatment study follow-up, and entered on the appropriate eCRF page.

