#### 10.3 OVERALL SURVIVAL

OS is defined as the time from enrolment to death due to any cause. OS will be expressed from time of enrolment in this study. Patients completing or withdrawing from the study will be followed up for post-study survival information until database lock and at this point, any patients without a death date will be censored at the date the patient was last known to be alive. The 1-year OS rate will be calculated.

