2.2.2 Secondary Endpoints

The secondary efficacy endpoints of the study are:

- PFS assessed by RECIST 1.1 after a maximum of 18 months treatment in patients receiving IMM-101 + nivolumab.
- OS and OS at 1 year, for both cohort A and cohort B. The median OS (if applicable) and OS rate at 12 months will be estimated.

The secondary safety endpoints of the study are:

- Incidence and frequency of laboratory parameter abnormalities.
- Change from baseline values in laboratory parameter values.
- Incidence and frequency of local injection site reactions.

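### The separate one-year OS analysis counts anyone without a death date as alive at one year, even if last known alive earlier

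*SAP*

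**What the plan says.** SAP Section 5.13.2.2 defines two OS analyses.

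- **Whole-study OS** censors a subject with no death date at the last date known alive, whether during or after the study.
- **OS at one year** is a second calculation, "where subjects without a death date will be right censored on the date of Visit 1 + 365 days". It has no clause for a subject whose last contact came earlier, and it does not say how deaths after one year are handled.

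Both analyses get descriptive statistics, a Kaplan-Meier (KM) plot and "KM estimates for the 25th, 50th and 75th percentiles for both OS and OS at one year". SAP Section 2.2.2 names the endpoint: "The median OS (if applicable) and OS rate at 12 months will be estimated". The SAP text does not say which of the two analyses supplies that 12-month rate.

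The protocol has a single censoring rule. Section 5.2.2, under the item covering both OS and OS at 1 year, says: "Patients without a death date will be censored at the date the patient was last known to be alive". Section 10.3 repeats it ("any patients without a death date will be censored at the date the patient was last known to be alive") and then refers to the 1-year rate. SAP Section 6 lists five changes from the protocol analysis; the one-year censoring rule is not among them.

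**The concern.** Right censoring should record how long a patient was actually observed alive. Moving the censoring date forward to one year credits a patient lost early with survival nobody observed. That patient stays in the denominator at each later death, each drop in the curve becomes too small, and the one-year estimate is too high. The error can only go upward.

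One-year OS is a named secondary endpoint, and the stated purpose of the study includes comparison with published efficacy data for nivolumab alone, so an upward bias flatters the combination. The rule is also out of line with the rest of the SAP. PFS and duration of response are censored at the last assessment, and subjects without a best overall response are assigned progression as a worst case. The one-year OS rule in effect assumes the best case without saying so.

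**Working it through.** The plan gives no one-year OS figure, assumed survival rate or loss rate, so there is nothing to reproduce. The check is a direct comparison of the two censoring rules.

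**Inputs from the documents.** Planned cohort sizes of 18 (A) and 8 (B), from SAP Section 3; the two censoring rules above; KM methods for OS, from Protocol Section 11.1.5.

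**Assumed inputs.** Number and timing of deaths and losses. Cohort B: deaths on Days 80, 200 and 300. Cohort A: deaths on Days 60, 120, 200, 260 and 320. All other patients are followed beyond Day 365 unless listed as lost.

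**Formula.** S(365) is the product of (1 − d/n) over death times up to Day 365, where d is the number of deaths and n the number still at risk.

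**As written.** Nobody leaves the risk set before Day 365 except by death, so the product collapses to (N − D)/N, with D first-year deaths, however many patients were lost:

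- Cohort B: (8 − 3)/8 = 62.5%
- Cohort A: (18 − 5)/18 = 72.2%

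**Censored at last known alive.** If L patients are lost before the first death, the product becomes (N − L − D)/(N − L).

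| Cohort | Losses | Calculation | Correct KM | As written |
|---|---|---|---|---|
| B | none | 5/8 | 62.5% | 62.5% |
| B | 1 before first death | 4/7 | 57.1% | 62.5% |
| B | 2 before first death | 3/6 | 50.0% | 62.5% |
| B | 1 at Day 250 | 6/8 × 4/5 | 60.0% | 62.5% |
| B | 2 after last death (Days 310, 320) | 5/8 | 62.5% | 62.5% |
| A | none | 13/18 | 72.2% | 72.2% |
| A | 1 before first death | 12/17 | 70.6% | 72.2% |
| A | 2 before first death | 11/16 | 68.8% | 72.2% |
| A | 3 before first death | 10/15 | 66.7% | 72.2% |
| A | 1 at Day 270 | 14/18 × 12/13 | 71.8% | 72.2% |
| A | 2 after last death (Days 330, 340) | 13/18 | 72.2% | 72.2% |

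The bias therefore needs a loss that precedes a later first-year death. Complete follow-up to one year is sufficient to avoid it but not necessary.

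**Deaths after one year (secondary).** Read literally, the sentence moves only subjects without a death date. Suppose Cohort A has the same 5 first-year deaths, a sixth on Day 420 and 12 patients alive. All 12 survivors are censored at one year, so only one patient is at risk on Day 420 and the curve falls from 0.722 to 0, giving a median of 420 days. Correctly, S(420) = 12/18 = 0.667 and the median is not reached. The one-year value is 0.722 either way. A percentile reached within the year is unaffected: with 8 patients, deaths on Days 50, 80, 150, 200, 300 and 420 and two alive, the median is 200 days under both rules.

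**The case against.** The best defence is that the practical effect may be nil.

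- **A correct analysis sits alongside.** Whole-study OS is properly censored, and the SAP also promises the proportion alive at 3-monthly intervals, which includes month 12. This limits the damage, but that sentence does not say which analysis it draws on, and the flawed analysis still produces its own statistics, percentiles and plot. The output shells are a separate document not seen here and may name the source.
- **Early loss may be rare.** The study runs until all patients have had the opportunity of 18 months of treatment, and survival is followed through the GP to database lock, including after withdrawal. This stands: zero loss is possible. But Protocol Section 6.7 provides for refusal of follow-up: "If a patient should wish to withdraw consent for future follow-up (as in Section 6.4) they should notify the Investigator of this decision".
- **The larger differences assume losses before the first death.** Also true. A single late loss costs 2.5 points in Cohort B (62.5 − 60.0) and 0.4 in Cohort A (72.2 − 71.8). Sampling error is far larger: exact 95% intervals are about 24% to 91% for 5/8 and 47% to 90% for 13/18.
- **The study is descriptive.** No test or decision rule depends on this figure. That limits the severity but does not justify the rule.
- **Late deaths may have been meant to be cut at one year.** That is the more natural reading, and on it the secondary problem disappears.

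None of this gives a reason to keep the sentence. Where nobody is lost, the correct rule returns the same number.

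**Conclusion.** The concern holds. The one-year OS rule in SAP Section 5.13.2.2 is wrong as written, departs from the protocol's single censoring rule, and is not declared in SAP Section 6. The error is confined to the second, one-year analysis.

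Under the assumed data the overstatement runs from 0 to 12.5 points in Cohort B (up to two losses) and from 0 to 5.6 points in Cohort A (up to three losses). It is zero if nobody is lost before one year or if every loss follows the last first-year death. These figures rest on assumed death and loss times, because the documents give none. The wording defect is certain; its effect on the reported result is not. The handling of deaths after one year is a lesser gap that leaves the one-year estimate unchanged. It should be corrected before analysis, in proportion to a descriptive secondary endpoint.

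**What to change.** Replace the one-year sentence in SAP Section 5.13.2.2 with wording such as: *OS at one year is the Kaplan-Meier estimate, with 95% CI, at 12 months from the whole-study OS analysis, in which subjects without a death date are censored at the date last known alive.* This also settles which analysis supplies the endpoint in SAP Section 2.2.2.

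If a separate truncated dataset is kept:

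- censor at the earlier of the last-known-alive date and the date of Visit 1 + 365 days;
- count deaths only up to Visit 1 + 365 days and censor later deaths there;
- report a percentile only if it is reached by then.

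List any remaining departure from the protocol in SAP Section 6. The cost is one sentence and one derivation, with no new data.

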5.13.3 Exploratory Endpoints

5.13.3.1 ORR assessed by irRC for Cohorts A and B

The analysis as detailed in Section 5.13.1 for the primary endpoint will be repeated where ORR is calculated from the BOR of subjects as assessed by irRC. Analysis will be performed on the ITT set for both cohorts.

For Cohort A, BOR is defined as the best response designation, recorded from the first post-baseline scan until and including the last scan on study for each subject.

For Cohort B, BOR is defined as the best response, recorded from the first post-baseline scan until and including the last scan on study for each subject for those receiving IMM-101 and nivolumab, or the last scan performed prior to treatment with ipilimumab. No scan performed once ipilimumab treatment commences will be included.

All scans within these defined periods, whether scheduled or unscheduled, will be evaluated for overall response.

Unconfirmed responses will be used in the assessment of BOR where BOR is the best overall response during the defined period and does not need to be confirmed at a subsequent timepoint.

Subjects without a BOR assessment, such as those with no post-baseline responses or only NE responses, will be assumed to have a response of PD using a worst-case approach.

ORR is calculated as the number of subjects with a BOR of CR or PR divided by the number of subjects in the analysis set. ORR is calculated for each cohort separately.

Summaries of BOR (irRC)

The BOR will be summarised for each cohort. The ORR and accompanying exact binomial 95% confidence intervals (CI) will also be presented.

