## **5.2.3** Exploratory Endpoints

The following additional exploratory endpoints, will be assessed at the end of the study and are:

- ORR using irRC for both cohort A and cohort B, assessed using BOR by irRC, with the same methods of calculation as for the primary endpoint of ORR (above).
- Duration of Response and Time to Response for both cohort A and cohort B, assessed by RECIST 1.1. For any patients in cohort B who change treatment on study to IMM-101 + ipilimumab, only responses evaluated until the point of this change in therapy are included.
- Disease Control, assessed for patients in cohort B of the study only, and defined as those patients with a response (CR or PR) or SD based on RECIST 1.1. and assessed at each scan assessment point from Week 14 onwards. Disease Control is evaluated for treatment with IMM-101 + nivolumab only and for any patients who change treatment to IMM-101 + ipilimumab, disease control is assessed until and including the last evaluable tumour assessment prior to the change in therapy.

- For the subgroup of patients in cohort B who receive IMM-101 + ipilimumab as subsequent treatment: the incidence, frequency and severity of adverse events, serious adverse events, treatment-related adverse events and immune-related adverse events (as listed in the SmPC for ipilimumab) experienced following the start of ipilimumab treatment up to the end of the study.
- To evaluate BOR for cohort B to include any responses obtained following a change in therapy from IMM-101 + nivolumab to IMM-101 + ipilimumab. All tumour assessments on study are included in this evaluation.
- Immunological markers from blood and biopsy samples from both cohorts A and B (to be reported separately to other endpoints).

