# **10.1.2 Best Overall Response**

Best Overall Response (CR, PR, SD or PD) is determined as the best response designation, recorded from the first post-screening scan until and including the last imaging assessment on study for each patient. All scans will be evaluated for overall response and BOR will be calculated based on overall response designations determined by the Investigator, from all scan assessments. However, for any patients in cohort B who change treatment on study to IMM-101 + ipilimumab, BOR will be assessed both before a change to ipilimumab for patients to whom this applies (for evaluation of ORR), and also from all tumour assessments on study.

BOR according to both RECIST 1.1 criteria and irRC criteria will be determined.

For cohort A, BOR will be assessed at the time point when all patients have had the opportunity for 12 months on study (RECIST 1.1 only), and again at the end of the study. For the first assessment, the BOR will be the best response designation, as determined by the Investigator, recorded from the first post-screening scan until the last scan prior to or at the 12 month time point for each patient on study.

For cohort B, BOR will be assessed at the time point when all patients have had the opportunity for 6 months on study (RECIST 1.1 only) and again at the end of study or when all patients in this cohort have withdrawn if this is sooner. For the first assessment, the BOR will be the best response designation, as determined by the Investigator, recorded from the first post-screening scan until the last scan prior to or at the 6 month time point for each patient on study. For any patients in cohort B of the study who change treatment on study to IMM-101 + ipilimumab, BOR will be assessed both before a change to ipilimumab for patients to whom this applies (for evaluation of ORR), and also from all tumour assessments on study.

In this study, the minimum scan time from Screening for determination of SD will be 9 weeks.

Confirmed response is used for calculation of BOR (Section 8.5.3.10); however unconfirmed results will also be analysed and corresponding BOR and ORR reported for comparability with published data.

Page 74 of 98

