# Exploratory efficacy endpoints:

- ORR assessed by irRC criteria for both cohorts at the end of the study
  The ORR will be calculated as for the primary endpoint, based on a BOR of CR or PR (by irRC criteria), see definition in Section 10.1.2 and presented as for the primary endpoint.
- Duration of overall response and time to response by RECIST 1.1, for both cohorts at the end of the study

Page 79 of 98

The duration of overall response is defined in Section 10.1.3 and time to response is defined in Section 10.1.4. These endpoints will be evaluated for responders only and will be summarised using KM methods and presented graphically where appropriate.

• Disease control rate (for patients in cohort B)

Disease control is defined in Section 10.6. The disease control rate will be assessed by assessment time point for patients in cohort B of the study only and is defined as the percentage of those patients with a response (CR or PR) or SD based on RECIST 1.1 and assessed at each scan assessment time point from Week 14 onwards to the end of the study (or to last scan prior to commencement of treatment with IMM-101 + ipilimumab if applicable).

• Best Overall Response for patients in cohort B, to include any responses during treatment with IMM-101 + ipilimumab

The BOR rate for cohort B will be assessed including any responses obtained following a change in therapy from IMM-101 + nivolumab to IMM-101 + ipilimumab. All tumour assessments on study (scheduled and unscheduled scan assessments) are included in this evaluation. The BOR will be listed by cohort B patient in this subgroup and the rate will be summarised using frequency counts and percentages.

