5.13.3.5 BOR Assessed by RECIST 1.1 for Cohort B Including Responses Obtained Following a Change in Therapy

The analysis as detailed in Section 5.13.1 for the primary endpoint will be repeated on Cohort B where ORR is calculated from the BOR of including assessments performed including scans performed following the change to treatment with IMM-101 and ipilimumab. Analysis will be performed on the ITT.

All scans over the entire study, whether scheduled or unscheduled, will be evaluated for overall response. Unconfirmed responses will be used in the assessment of BOR where BOR is the best overall response during the defined period and does not need to be confirmed at a subsequent timepoint. Subjects without a BOR assessment, such as those with no post-baseline responses or only NE responses, will be assumed to have a response of PD using a worst-case approach.

Summaries of BOR in Cohort B (including assessments post ipilimumab)

The BOR will be summarised and the ORR and accompanying binomial 95% CIs will also be presented.

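### SAP 5.13.3.1 bases the irRC response rate on unconfirmed responses only, against the protocol's instruction to calculate it as the confirmed primary ORR is calculated, and SAP Section 6 does not declare the change

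*SAP*

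**What the plan says.** **Protocol, irRC ORR.** Section 5.2.3 defines this exploratory endpoint as "assessed using BOR by irRC, with the same methods of calculation as for the primary endpoint of ORR (above"). Section 11.1.5 says the same: "The ORR will be calculated as for the primary endpoint, based on a BOR of CR or PR" by irRC, and refers to Section 10.1.2 for the definition. Section 10.1 also says the irRC rate is calculated in a similar way to the primary one.

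**Protocol, best overall response.** Section 10.1.2 covers BOR under both RECIST 1.1 and irRC, and also the Cohort B BOR that takes in scans after a switch to ipilimumab. Its rule is "Confirmed response is used for calculation of BOR (Section 8.5.3.10); however unconfirmed results will also be analysed and corresponding BOR and ORR reported".

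**Protocol, confirmation scans.** Section 8.5.3.10 requires confirmation of CR and PR for RECIST 1.1, at least 4 weeks later. For irRC it leaves confirmatory scans to the investigator as an aid to managing treatment. Section 5.3 repeats this, and also has both criteria recorded in the eCRF for every scan.

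**SAP.** Section 5.13.1 derives the primary BOR from confirmed responses. Sensitivity analysis 1 in that section repeats the table with confirmed or unconfirmed RECIST responses. Section 5.13.3.1 announces a repeat of 5.13.1 for irRC and then states "Unconfirmed responses will be used in the assessment of BOR". Section 5.13.3.5 does likewise for the Cohort B BOR including ipilimumab: "Unconfirmed responses will be used in the assessment of BOR where BOR is the best overall response during the defined period". Section 6 lists five changes from the protocol, and neither of these is among them.

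**The concern.** The irRC endpoint is useful mainly for showing whether immune-related criteria pick up responses that RECIST 1.1 does not. If the irRC rate rests on unconfirmed responses and is compared with the confirmed primary ORR, two changes are mixed: the criteria and the confirmation rule. A reader who relies on SAP Section 6 would assume that the irRC table follows the protocol and could credit the whole difference to the criteria.

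The Cohort B table in 5.13.3.5 carries a similar risk. A patient with one unconfirmed PR on nivolumab who never received ipilimumab would count there but not in the primary ORR. The extra responder could be taken for a gain from including the scans after the switch.

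**Working it through.** The documents give no sample size derivation and no confirmed-versus-unconfirmed figure, so there is nothing to reproduce. The check is a comparison of the texts, followed by arithmetic for scale.

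**Step 1. Rules side by side**

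| Quantity | Protocol basis | SAP basis | Listed in SAP Section 6? |
|---|---|---|---|
| Primary ORR, RECIST 1.1 | Confirmed, with unconfirmed in addition (10.1.2, 11.1.5) | Confirmed, with unconfirmed as sensitivity analysis 1 (5.13.1) | No change to list |
| irRC ORR | As for primary (5.2.3, 11.1.5); 10.1.2 covers both criteria | Unconfirmed only (5.13.3.1) | No |
| Cohort B BOR including ipilimumab | General rule of 10.1.2 only | Unconfirmed only (5.13.3.5) | No |

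**Step 2. Direction.** Fix the criteria, the scans and the ITT denominator n. Patients with a confirmed CR or PR are a subset of those with any CR or PR. If k responders are not confirmed, then

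unconfirmed ORR − confirmed ORR = k/n ≥ 0.

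**Step 3. Size per patient.** The planned sizes are 18 and 8 (Protocol 11.2; SAP Section 3).

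- Cohort A: 1/18 = 5.6 points.
- Cohort B: 1/8 = 12.5 points.

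**Step 4. Illustration with exact (Clopper-Pearson) 95% intervals.** The counts are assumed.

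| Cohort | Responders | ORR | 95% CI |
|---|---|---|---|
| A | 8/18, all counted | 44.4% | 21.5 to 69.2 |
| A | 7/18, one not confirmed | 38.9% | 17.3 to 64.3 |
| A | 6/18, two not confirmed | 33.3% | 13.3 to 59.0 |
| B | 2/8, all counted | 25.0% | 3.2 to 65.1 |
| B | 1/8, one not confirmed | 12.5% | 0.3 to 52.7 |

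**Step 5. Range for Cohort A.** Let u be the unconfirmed rate and f the share of responders not confirmed. Take u = 44% for illustration, borrowed from the nivolumab rate in Protocol 3.4. The documents do not give f, so 0 to 30% is assumed. The confirmed rate is u(1 − f), the gap is uf, and the chance of at least one unconfirmed-only responder among 18 is 1 − (1 − uf)^18.

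| f | Confirmed rate | Gap | Chance of at least one |
|---|---|---|---|
| 0% | 44.0% | 0 points | 0% |
| 10% | 39.6% | 4.4 points | 55.5% |
| 20% | 35.2% | 8.8 points | 80.9% |
| 30% | 30.8% | 13.2 points | 92.2% |

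**Step 6. Could the confirmation rule be visible beside the effect of the criteria?** PR needs a 30% fall in the sum of diameters under RECIST 1.1 (Protocol 8.5.3.1) and a 50% fall in the sum of products under irRC (8.5.3.2). A uniform 30% fall in diameter gives 1 − 0.7² = 51% in the product. On the same uniformly shrinking lesions the thresholds nearly coincide, so a different confirmation rule could make up much of an apparent gap. New lesions and the different numbers of lesions followed also separate the two criteria.

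**Step 7. Can confirmed irRC be derived?** Both criteria are recorded at every scan. RECIST responders should have a repeat scan at least 4 weeks later, and other patients are scanned every 8 weeks, with 12-weekly scans allowed after Week 52. A confirmed irRC status therefore follows from existing data whenever a later evaluable scan exists.

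**The case against.** The strongest reply is that the protocol does not clearly demand confirmed irRC responses. Section 10.1.2 cites 8.5.3.10, and there the requirement is confined to RECIST 1.1 while irRC confirmation scans are optional. On that view, calculating as for the primary endpoint means only responders with CR or PR over the ITT count. This stands in part. A reader might infer that the SAP broke an unambiguous protocol rule, but the documents do not support that, because the protocol pulls two ways. The reply does not clear the SAP, however. The optional-scan text concerns which scans to order, not how BOR is derived; 10.1.2 names both criteria; and 5.13.3.1 contradicts its own promise to repeat 5.13.1.

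Other points on that side also stand:

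- The protocol's wording on same methods covers the irRC ORR only. For the Cohort B BOR including ipilimumab, the mismatch is with the general rule of 10.1.2 and with the SAP's own repeat wording.
- Sensitivity analysis 1 is a like-for-like unconfirmed RECIST comparator, and no section instructs the reader to set the irRC table beside the primary ORR.
- Switching to ipilimumab requires no prior recorded response, and the BOR listing shows confirmed, unconfirmed and post-switch RECIST results by patient. This limits misreading in Cohort B.
- The SAP states the unconfirmed basis openly, and Protocol 11.6 allows deviations to be documented in the SAP. What is missing is a justification and an entry in Section 6.
- Some irRC-only responses will have no later scan, because extra irRC scans are optional, the end-of-study scan is conditional, and Cohort B scans stop counting for irRC at the switch. A confirmed irRC rate would then err somewhat low.
- Both endpoints are exploratory and descriptive, so no error rate is affected.

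**Conclusion.** The point holds as a conflict between protocol and SAP, complicated by an ambiguity within the protocol. The SAP uses only unconfirmed responses for the irRC ORR, plans no confirmed version, and does not list the choice in Section 6. The weaker mismatch in 5.13.3.5 is with Protocol 10.1.2 and with the SAP's own wording.

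The effect of the confirmation rule has a known direction and an unknown size: zero or upward, at 5.6 points per unconfirmed responder at n=18 and 12.5 at n=8. The 0 to 13.2 point range for Cohort A rests on the assumed 44% rate and the assumed 0 to 30% share not confirmed.

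Two stronger readings go too far. A reader might infer that the irRC rate will be inflated, but every responder may be confirmed, and a difference from RECIST also reflects the criteria. A reader might also apply the steps for the 11 and 5 patients of the interim reviews, but irRC response is not assessed there. What follows is that the planned irRC rate should not be read against the confirmed primary ORR.

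**What to change.** 1. Reconcile Protocol 5.2.3, 11.1.5 and 10.1.2 with 8.5.3.10, so that one statement says whether irRC BOR needs confirmation.
2. In SAP 5.13.3.1 and 5.13.3.5, add a confirmed irRC BOR/ORR table and a confirmed Cohort B all-scan BOR table from scans already collected. Use the 5.13.1 rule: a CR or PR upheld on an evaluable scan at least 4 weeks later, with the existing PR-NE-PR handling. PR followed by CR counts as a confirmed response; a rule demanding the identical category again would wrongly reject it.
3. Keep the unconfirmed tables, label them as unconfirmed, and pair them with RECIST sensitivity analysis 1. In Cohort B this pairing also isolates what the scans after the switch add, since both tables are then unconfirmed.
4. List the choice, with its reason, in SAP Section 6.

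The cost is SAP wording and one or two extra tables, with no added scans. The downside is that some irRC-only responses may lack a later scan and count as unconfirmed, so the confirmed irRC ORR may be somewhat lower. A footnote should say so and give the number of such patients.
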